The study design of TOHP is fairly complex, owing to the large number of diverse interventions being tested. The 10 clinical centers are each testing a different combination of interventions, although they can be divided into three broad categories: clinics offering only a combination of lifestyle interventions (sodium reduction, weight loss, and stress management, plus a control group); those offering only supplements (calcium and magnesium and their placebos in Stage 1, fish oil and potassium and their placebos in Stage 2); and "hybrid" clinics offering both types of intervention. Specific clinic allocations and the approximate numbers of subjects that will be assigned to each study group if recruitment goals are met are shown in Table 1.

For the lifestyle interventions, an open design is being utilized. After the initial orientation at randomization, those individuals assigned to the control

group will be invited to the clinic for data collection visits only. Because of this design feature, particular care will be taken to maintain blindness to intervention assignments among all clinic personnel involved in collecting any study data, especially BP. To avoid differential habituation to the BP measurement environment, data collection and intervention sessions should also take place in physically separate locations if at all possible. For the supplements interventions, placebo control has been adopted so that double blindness will be maintained.

ELIGIBILITY AND EXCLUSION CRITERIA

The general aim of the eligibility and exclusion criteria in TOHP is to assemble a group of healthy, non-hypertensive individuals who can safely undertake the study interventions and who are likely to be cooperative with follow-up requirements for the duration of the trial. In order to establish an overall study cohort that is generally comparable across all clinical centers, it is necessary to have generally uniform eligibility and exclusion criteria for all participants, regardless of which interventions an individual clinic may be testing.

Specific eligibility and exclusion criteria are outlined below.

Eligibility Criteria

1. Diastolic Blood Pressure

At each of the three screening visits, DBP will be determined as an average of all screening BPs obtained up to that time (three per visit), with the average falling within a specified range for a subject to be eligible. These ranges are:

Screening visit #1: DBP 75-97 mm Hg (3 readings)

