A 24-hour urine sample will be collected at each of the SV3 and the status review visits. The first of these will be used as a behavioral compliance measure. Both samples will be analyzed at a central laboratory for baseline values. At lifestyles clinics testing the sodium reduction intervention, the baseline 24-hour urine samples will collect the overnight and daytime samples separately. 24-hour urine samples collected during follow-up will be used to assess compliance with the assigned interventions and to provide descriptive indices of mean intakes of the nutrients of interest. 24-hour urine samples will be collected at 6, 12, and 18 months for the lifestyle participants (FO2, FO9 and F16). For supplements participants 24-hour urine samples will be obtained at the beginning of Stage 2 and at 3 and 6 months post randomization in both Stages 1 and 2 (FO1, FO2, FO7, F12, F13).

Blood and urine tests for the lifestyles and supplements interventions are summarized in Tables 4 and 5, respectively.

10. Pill Count

As a compliance measure in the supplements interventions and their comparison groups, all participants will be asked to bring their calendar packs to all follow-up visits so that the number of pills taken since the previous data collection visit can be determined and recorded by study personnel.

Intervention-specific data to be collected at baseline and follow-up visits (e.g., skinfold/circumference measurements and physical fitness testing) are included in the following chapter on intervention methods.

INTERVENTION METHODS

From an operational viewpoint, there are four major intervention groups in TOHP: sodium reduction, weight reduction/exercise, stress management, and the

supplements. All of the intervention groups will use a case-management approach in which each participant will be assigned to a specific interventionist. The interventionist will be responsible for monitoring the participant's progress in achieving the study objectives and for initiating appropriate actions when problems arise.

-22-

The objectives and intervention strategies for each of the intervention groups are briefly described below.

Sodium Reduction

1. Objective

The objective for participants randomized into the low sodium group is to maintain an eating style that does not exceed 1400 mg (60 mEq) sodium daily over a two-year period. The goal for the group is to achieve a mean of 1800 mg (80 mEq) sodium daily based on urinary excretion data.

2. Approach

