As health questions arise, particularly those pertaining to the benefits of any of the active interventions, a TOHP staff member assigned to be the case manager for the control subjects should answer the questions. In giving such explanations, it should be pointed out that the lifestyle changes in question have not been proven to be effective for people in the upper-normal range of BPs, and that it is the objective of TOHP to determine whether this is, in fact, the case.

If at any time a participant should express a desire to attempt a lifestyle change, such as losing weight, the TOHP staff involved should reiterate that the purpose of the comparison group is to permit observation of BP levels in individuals not undergoing any lifestyle changes, and that TOHP would not be able to support them in such an effort. They should be requested to forego such lifestyle changes temporarily, if possible, for the duration of the study.

Although the approach recomended here will not guarantee that lifestyle control subjects will refrain from attempting lifestyle changes, it should be effective in keeping the conscientious participant from actively pursuing such changes. Even if a lifestyle change is initiated, the probability is that such an attempt will be only transient and that the old eating habits or other behaviours will return over time.

3. The Intervention

The intervention for the lifestyle control group is, ideally, to maintain the status quo. TOHP is organized so that all participants in this group will serve as controls for all lifestyle interventions at a particular clinical center. For example, if a center is offering stress management and sodium restriction, then the lifestyle control group at that center would provide comparisons for both interventions and undergo all intervention-specific protocols pertinent to those interventions. The one exception is that for comparisons involving the weight loss intervention, the controls will be drawn from individuals at the clinical center who, like those randomized to that intervention, are in the high weight stratum.

4. Measures to Enhance Compliance

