The final approach to maintaining high attendance and compliance among the lifestyle control group involves making clinic visits as convenient, brief, and comfortable as possible. The responsibility for accomplishing this objective rests on the data collectors and the case managers at the clinic. In addition to administering the required protocols, data collection personnel must work efficiently and maintain friendly interactions with the participants. They must also make every effort to remain blinded to the intervention in which a participant is involved so that possible biases can be minimized. It is essential that the data collectors should not answer health questions that arise during the course of the study. Instead, a nurse or other health professional who is not involved in data collection should be made available to answer any such questions as they arise.

The case manager will function as a link between the study staff and each TOHP participant. The establishment of rapport between the case manager and the lifestyle controls is particularly crucial because such

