participants will not have frequent contact with an interventionist or intervention group members. The case manager will make all appointments, check the participant in and out of the clinic, and answer questions about the study that arise. Ideally, this position should be held by a nurse or other health professional. The case manager may wish to keep an updated index card on each lifestyle control, including any problems a participant may be having with the study, the most convenient times for clinic visits, as well as some personal facts and a photograph of that individual to permit personalized interactions. This information should facilitate the development of a positive relationship between each individual in the lifestyle control group and his or her case manager. For example, the personal information on the index card, which should include notes about that individual's hobbies, recent vacations, family members, etc., may be used as a source for informal conversations during the check-in or check-out process. The individual attention that such interactions provide will serve to convey to the participants in the lifestyle control groups that someone on the study staff cares and appreciates his or her participation. Other trials have found that such an approach was extremely effective in maintaining high compliance with scheduled visits. This method, coupled with the benefits of regular BP monitoring, the availability of detailed health information, and the contribution of participants to the public health, should maximize motivation and compliance in the lifestyle comparison group.

Supplements

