a. Prior to Stage 2, individuals with a bleeding history will be identified based upon responses to the Supplements Form administered at SV3, SRV, 6 weeks, 13 weeks, and 26 weeks and reviewed by a clinic physician. Those individuals identified by the clinic physician as having a potential bleeding disorder based upon responses to the follow-up forms, will be asked to undergo evaluatory tests for

bleeding time, platelet count and VWF level for possible exclusion from Stage 2 based upon a history of recurrent abnormal bleeding.

- b. Individuals identified by the clinic physician as having a potential bleeding disorder, who do not wish to submit themselves to testing, will be excluded from Stage 2.
- c. During Stage 2, individuals assigned to the fish oil component who develop a bleeding history based upon responses to the Supplements form administered at 6 weeks and 13 weeks of Stage 2 or other self-reports will have their case reviewed by a clinic physician. If in the judgement of the physician it is clinically warranted, the individual will be asked to undergo tests immediately to evaluate the bleeding problem. Participants will be asked to discontinue their pills for the duration of the trial if, in the opinion of the clinic physician, the tests reveal an abnormal bleeding problem or if the participant refuses to undergo the recommended evaluation procedures.

ASCERTAINMENT OF ENDPOINTS

Both primary and secondary outcomes for TOHP are determined from measurements and laboratory tests taken at follow-up visits; therefore, ascertainment of endpoints is relatively simple and straightforward. Outcome measurements will be made by data collectors blinded to the treatment assignment of participants and not involved in delivering any lifestyle intervention. Due to the subjective nature of BP measurement, it is particularly important that the BP observers are not involved in any way with the delivery of any intervention and have no access to intervention-specific data. Insofar as possible, data collection visits should take place on different days and at different locations from intervention visits so that those in the active intervention groups do not become more habituated to the data collection environment than those in the comparison group.

Ascertainment of Blood Pressure

The outcome of primary interest, for which the sample size and power calculations were performed, is diastolic BP; a major secondary endpoint is

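### Lifestyle controls are given personal rapport contact at check-in or check-out of their BP visits, with no matching provision for the active arms and no rule that it follow the readings

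*Protocol*

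**What the plan says.** **Controls.** Study Design states that, after orientation, the control "group will be invited to the clinic for data collection visits only". Under Lifestyle Control Group, Approach, health questions are directed to a designated person: "a TOHP staff member assigned to be the case manager for the control subjects should answer the questions". Under Measures to Enhance Compliance in the same section, the role is described as follows: "The case manager will make all appointments, check the participant in and out of the clinic, and answer questions about the study that arise". On rapport it says: "The establishment of rapport between the case manager and the lifestyle controls is particularly crucial because such" participants have little contact with an interventionist or group. The case manager may keep an index card on each lifestyle control, holding scheduling notes, personal facts and a photograph. The personal information "may be used as a source for informal conversations during the check-in or check-out process".

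**Active arms.** The opening of Intervention Methods says: "All of the intervention groups will use a case-management approach in which each participant will be assigned to a specific interventionist". The protocol does not say who checks these participants in at data collection visits, and it provides no index card or rapport conversation for them there.

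**Safeguard.** Ascertainment of Endpoints says: "Insofar as possible, data collection visits should take place on different days and at different locations from intervention visits", and gives the reason: "so that those in the active intervention groups do not become more habituated to the data collection environment than those in the comparison group". Study Design makes a similar, equally conditional request about physical separation. Both sections require data collectors to be blinded to assignment.

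**The concern.** The lifestyle comparison is open, so its validity depends heavily on BP being taken under the same conditions in every arm. The protocol accepts this. It treats unequal habituation to the measurement setting as something to prevent, and under Ascertainment of Blood Pressure it lists emotional state among the causes of BP variation. The safeguard, however, is written in one direction only. The control section then provides a friendly, personalised contact on the day of measurement for controls alone.

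Two things are at stake. First, if the contact comes before the readings and changes how relaxed controls are, the change enters the follow-up BP of one arm only. Second, if controls are visibly received by a known control case manager and others are not, data collectors at the clinic may learn the arm.

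**Working it through.** **Step 1. Does the contact fall on BP visits?** Controls attend data collection visits only (Study Design). Three BP readings are taken at every visit except SRV and FO8 (Follow-Up Schedule), so control check-in and check-out during follow-up occur on days when BP is read.

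**Step 2. Is it specific to controls?** In part. The sentence on check-in refers to the participant in general, and the sentence introducing the role links the case manager to every trial participant. The index card and the emphasis on rapport are written for lifestyle controls.

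**Step 3. Is the order fixed?** No. The conversation may take place at check-in or at check-out. Only the first could influence the readings, and the text leaves the choice open.

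**Step 4. Would the change score cancel a shift?** No. Baseline DBP comes from SV1 to SV3, before assignment. The primary lifestyle outcome is change from that baseline to 18 months (Data Analyses). A contact that exists only after assignment affects only the follow-up term. Averaging nine readings over three visits reduces random error but not a systematic shift.

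**Step 5. What would a shift do to power?** The documents give no size, so the shifts below are assumptions. Inputs from Power Calculations: DBP and Table 12 are an SD of change of 6.36 mm Hg, two-sided alpha 0.05, a difference of 2 mm Hg, and active/control numbers of 327/416 (sodium), 308/232 (weight) and 242/319 (stress).

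SE = 6.36 × √(1/n₁ + 1/n₀)

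- Sodium: 6.36 × √(1/327 + 1/416) = 0.470
- Weight: 6.36 × √(1/308 + 1/232) = 0.553
- Stress: 6.36 × √(1/242 + 1/319) = 0.542

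Power = Φ(d/SE − 1.96), where Φ here is the lower-tail normal probability. With no shift (d = 2), sodium is Φ(4.255 − 1.96) = .989, weight .951 and stress .958. Table 12 prints .99, .95 and .92. The first two reproduce. The stress row does not: its printed 80%-power difference is 1.66 against 1.52 by the formula. That has no bearing on this point.

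With a true effect of 2 mm Hg and an assumed net lowering of control DBP at follow-up:

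| Assumed net shift (mm Hg) | Difference seen (mm Hg) | Sodium | Weight | Stress |
|---|---|---|---|---|
| 0 | 2.00 | .99 | .95 | .96 |
| 0.25 | 1.75 | .96 | .89 | .90 |
| 0.5 | 1.50 | .89 | .77 | .79 |
| 1.0 | 1.00 | .57 | .44 | .45 |

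A net shift in the other direction would enlarge the apparent difference instead: 0.5 mm Hg would turn a true 2.0 into 2.5. The table shows how sensitive the comparison is. It does not predict a loss.

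**The case against.** A reader might infer three stronger things that the documents do not support.

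- **That active participants' case managers are kept away from BP visits.** No sentence says so. The explicit bar is on BP observers delivering interventions or seeing intervention data, and the separation of visits is conditional. In the maintenance phase of Sodium Reduction, participants are to be seen in conjunction with data collection visits, within the separation constraint. The case manager is also described as a link to every participant, so check-in by a case manager may apply in all arms.
- **That the bias runs toward zero.** The net sign is unknown. Active participants come to the clinic far more often: 14 weekly sessions then monthly meetings for weight, 23 sessions for stress, and at least 14 group and 5 individual contacts for sodium. The protocol itself worries about their greater familiarity, and rapport with controls may partly offset it.
- **That power will fall.** The shifts in the table are assumed. Any bias of the same size would give the same figures.

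Other points also have force. The card and the conversation are optional, and the talk may come after the readings. BP is taken under a uniform preparation protocol with random-zero devices and blinded observers. The contact also serves retention in a group whose drop-out the protocol regards as a serious problem.

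These arguments limit the claim but do not remove it. Blinded observers and random-zero devices address observer bias, not the participant's own state. Optional use adds variation between clinics. An unmeasured offset between two arm-dependent influences is a weaker protection than having the same routine in every arm.

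**Conclusion.** The point holds in a limited form. The protocol provides control-specific rapport contact on BP-measurement days, does not fix it after the readings, and has no corresponding provision for the active lifestyle arms. Its habituation safeguard covers only the opposite imbalance. The arrival routine may therefore differ by arm and may give blinded data collectors a cue to assignment.

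The size and net direction of any effect on the DBP difference cannot be determined from the document, so neither a bias toward the null nor a loss of power has been shown. The power figures rest entirely on assumed shifts. The point concerns the three open lifestyle comparisons and not the placebo-controlled supplements. Severity is low; it merits a change because the change is inexpensive.

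**What to change.** In Lifestyle Control Group, Measures to Enhance Compliance:

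1. State that check-in at every data collection visit follows the same routine for all lifestyle arms, including controls.
2. Place the control case manager's personal conversation, use of the index card and answering of questions at check-out after the last BP reading, or by telephone between visits.
3. Reconcile this wording with the case-management statement that opens Intervention Methods, the maintenance-phase contacts under Sodium Reduction, and the separation rule in Ascertainment of Endpoints, so that it is clear who meets active participants at BP visits.

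The cost is a wording change and some rearrangement of existing staff duties. Controls receive a slightly less personal welcome on arrival. The retention contact itself is kept, which matters given the protocol's concern about control drop-out.

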The supplements to be tested in TOHP include calcium, magnesium, potassium, and fish oil (the only agent for which an Investigational New Drug approval is necessary). For subjects in the supplements arm of the trial, the total study period will be divided into two sequential phases of six months duration interrupted by a three-month wash-out period during which subjects will be maintained on placebos of their assigned Stage 1 agent. A set of entry and termination BP measurements will be obtained for each of the active intervention phases. Calcium and magnesium will be tested during Stage 1. Participants will be randomized to one of four regimens: calcium, magnesium or their respective placebos. Since the placebo controls are shared (i.e., the same group of controls serves as the comparison series for both the active calcium and the active magnesium groups), approximately half of those randomized to the control

group will receive placebo calcium and the other half will receive placebo magnesium. For Stage 2, participants who are still willing and eligible to continue will be randomly assigned to either fish oil, potassium, or their respective placebos. As with Stage 1, the placebo controls will be shared.

1. Dosages

The dosages selected for calcium, magnesium and potassium represent an approximate doubling of usual dietary intake in Western countries. The dose of fish oil is equivalent to that which would be obtained by ingesting approximately a half pound of salmon per day and is consistent with a level of supplementation that could be achieved by diet. The specific dosages and number of daily pills required for each of the supplements are as presented in Table 11.

All supplements will be administered in two doses per day, taken in the morning and evening, as this schedule is more convenient for participants than more frequent administration and thus more likely to enhance compliance. For calcium, magnesium, and fish oil, the pills will be divided into two equal doses. For potassium, participants will be instructed to take two pills in the morning and one in the evening to minimize the likelihood of esophageal irritation. A missed morning dose can be made up in the evening, and a missed evening dose can be made up the following morning; however, participants should never take more than a full daily dose at one time.

2. Run-In

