In addition to the behavioral compliance measures that have been described previously, there will be a pre-randomization run-in period for the supplements arm of the trial. The purpose of the run-in is to allow individuals likely to become non-compliant to the study regimens to be eliminated prior to randomization. During the run-in, potential participants will have an opportunity to try a pill-taking regimen similar to that which will be required during the active intervention phases. This strategy has particular applicability to the supplements arm of TOHP, since the use of placebo control and the lack of major side-effects associated with any of the supplements make it possible to test the exact intervention regimen

11/7/88

(i.e., pill taking) prior to randomization without contaminating the study groups.

Magnesium placebo capsules (six per day) will be used for the run-in. Magnesium placebos were chosen because they are relatively large and six is the maximum number of pills per day which a participant will be required to take in either the first or second testing periods. Thus, it is anticipated that participants able to comply with this pill-taking regimen will also be able to comply with any of the other supplement regimens involving fewer numbers and smaller capsules or tablets.

Clinic Procedures

All participants randomized to the supplements arm of the trial will be assigned to a specific health counselor who will see them individually at each intervention visit and who will be responsible for tracking their progress in achieving the study objectives. The nature of the counseling sessions will be tailored to the individual and could include specific instruction regarding the administration of the supplements, positive reinforcement, motivational talks, videotapes and discussion of suspected side-effects.

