- Pills will be packaged in convenient calendar packs.
- b. Individual instruction regarding administration of the supplements, positive reinforcement, and/or discussion of suspected side effects and what to do about them will be provided by the participant's health counselor, preferably a nurse with experience in reinforcing medication compliance among patients.
- c. Calendar packs will be dispensed in such a manner that the participant will have a sufficient supply of pills to last from one follow-up

visit to the next. An additional card will be dispensed at the beginning of each phase to serve as a reserve pack in case a visit is missed or a card lost.

d. At the beginning of the trial each participant will be provided with a set of study guidelines as an aid to compliance. The guidelines will cover such topics as what to do if calendar cards are lost, how and when to take the supplements, what multivitamins and supplements to avoid, and what to do if suspicious of side-effects.

Side Effects

Because of the benign nature of the supplement interventions, we expect a low incidence of side effects attributable to the study pills, although they will be monitored at the follow-up visits. The major potential concern in this regard is the possibility of bleeding problems among individuals assigned to fish oil. Specific procedures pertaining to safety monitoring of the fish oil component are described below.

At each follow-up session a health counselor will discuss with the participant any reported side-effects attributed to the pills. When necessary, the participant will be referred to a licensed physician on the clinic staff who will respond to each individual case using his or her best clinical judgment. In general, participants will be advised to seek medical attention from their own physician as needed and may alter their participation in the light of such counsel. Every effort will be made to maximize compliance consistent with the health and welfare of the participant.

The following procedures have been adopted to monitor the safety of those taking fish oil supplements.

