Session 9

Review of First Food Exchange Diaries Healthy Eating (U.S. Dietary Goals) Individual Planning Supervised Exercise

Session 10

Food Exchange Scoring System Self-reinforcement techniques Individual Planning Supervised Exercise

Sessions 11-14

Outlines to be developed. All of these sessions will include: Individual Planning Supervised Exercise

-FINAL TOHP STRESS MANAGEMENT PROGRAM COMPONENT SEQUENCING

MONTH	SESSION	TYPE	Weekly Sessions	
M01	01		Individual orientation & intervention data collection	-
M01			Group building + Slow-Paced Breathing	-
1	03	1 1	Bernstein & Borkovec Progressive Muscle Relaxation (B&B PMR) #1	1 1
	[04		B&B PMR #2: Emphasis on minimal tension & applications	1
	05		Relaxation using Imagination	1 (
M02			Applied Relaxing Imagination: Desensitization	1
M02			Applied Relaxing Imagination: Positive Covert Rehearsal	MI
M02	08	G	Clinically Standardized Meditation (CSM)	
			Biweekly Sessions	
М03	09	G	Time Management #1	
	10			M2
M04	11	G		
M04	12	G	Changing Stressful Thinking Patterns #1	
			Monthly Sessions	
MO5	13	G	Changing Stressful Thinking Patterns #2	1
M06	14	I	Individual session. Focus: Long term maintenance & applied skills	
	15			1 1
M08	16	G	Positive Cognitive Coping Strategies	1
	17			1.3
M10	18	G	Active Listening + Assertiveness Training #2	op [
			Anger Management #1	M4
M12	20	G	Anger Management #2	
			Bimonthly Sessions	
M14	21	G	General Problem Solving Session #1	45
	22		General Problem Solving Session #2	146
M18	23	G	General Problem Solving Session #3	M 7

Type: G or I: Type of session, group or individual

M1, etc.: Represents 10 min. segment on long term maintenance

Table 11

DOSAGES AND NUMBER OF DAILY PILLS REQUIRED FOR TOHP SUPPLEMENTS INTERVENTIONS

Supplement	Dosage/Day	Dosage/Pill	Pills/Day
Calcium carbonate	1000 mg	500 mg	2
Magnesium diglycine	360 mg	60 mg	6
Potassium	60 mmoles	20 mmoles	3
Fish oil*	3000 mg	500 mg	6

^{* 1000} mg capsule of Promega contains 500 mg of fish oil.

Table 12
SAMPLE SIZE AND POWER ESTIMATES: DBP

	Size of Comparison		Average	Δ for	
Intervention	Active	Control	Expected Follow-up	80% Power (mm Hg)	$\Delta = 2 \text{ mm Hg}$
Sodium Restriction	327	416	18 months	1.32	.99
Weight Reduction	308	232	18 months	1.55	. 95
Stress Management	242	319	18 months	1.66	. 92
Calcium	237	234	6 months	1.60	.94
Magnesium	227	234	6 months	1.61	. 94
Potassium	207*	203*	6 months	1.70	.91
Fish oil	199*	203*	6 months	1.72	. 90

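### The missed-dose rule lets a participant take all three potassium pills in the evening, although the schedule puts only one there to limit esophageal irritation

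*Protocol*

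**What the plan says.** The Protocol's Intervention Methods chapter (Supplements, 1. Dosages) sets the schedule in one paragraph. All four supplements follow a two-intake day: "All supplements will be administered in two doses per day, taken in the morning and evening". Three of them are split evenly: "For calcium, magnesium, and fish oil, the pills will be divided into two equal doses". Potassium is treated separately, and a reason is given: participants are to "take two pills in the morning and one in the evening to minimize the likelihood of esophageal irritation".

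The rule for missed doses comes next and names no supplement: "A missed morning dose can be made up in the evening, and a missed evening dose can be made up the following morning". Its one limit is that "participants should never take more than a full daily dose at one time". Table 11 lists potassium at 60 mmol a day in three pills of 20 mmol.

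Two other places touch on how pills are taken. Under Clinic Procedures, individual counseling "could include specific instruction regarding the administration of the supplements". Under Measures to Enhance Compliance, written guidelines are to cover topics including "what to do if calendar cards are lost, how and when to take the supplements". Neither place states a separate make-up rule for potassium.

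**The concern.** Potassium is the only supplement whose intake pattern is fixed by a tolerability precaution. The make-up rule fits the other three, which carry no such precaution, but it is applied to potassium unchanged. Its ceiling is a full day's pills, and one made-up dose plus the scheduled dose always equals exactly that, so the ceiling never stops a single make-up.

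The Protocol does not say whether the precaution was meant to limit the number of pills swallowed together or to keep the evening intake small. Three pills in the evening defeats it either way. Three pills in the morning after a missed evening dose defeats it only if the aim was to limit pills per intake.

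At stake is participant safety on make-up days in Stage 2: someone following the written instructions exactly could take the whole day's potassium at the time the Protocol chose to keep lightest. The primary endpoint, the power calculations and the error rates are untouched.

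**Working it through.** **Inputs.** The split and the make-up rule come from the Dosages section; pill counts and strengths come from Table 11.

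**Reproducing the plan's figure.** 60 mmol a day ÷ 20 mmol per pill = 3 pills a day, which matches 2 (morning) + 1 (evening).

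**The ceiling.** One full daily dose of potassium = 3 pills = 60 mmol.

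**Intake after one missed dose.** Made-up intake = scheduled pills at that time + missed pills. The ratio is made-up intake ÷ scheduled intake.

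| Regimen | Missed dose | Scheduled at make-up time | Intake with make-up | Ratio | Within ceiling? |
|---|---|---|---|---|---|
| Potassium | morning (2) | 1 pill, 20 mmol | 1 + 2 = 3 pills, 60 mmol | 60/20 = 3.0 | yes, equal to it |
| Potassium | evening (1) | 2 pills, 40 mmol | 2 + 1 = 3 pills, 60 mmol | 60/40 = 1.5 | yes, equal to it |
| Calcium | either (1) | 1 pill | 1 + 1 = 2 pills | 2.0 | yes, equal to it |
| Magnesium | either (3) | 3 pills | 3 + 3 = 6 pills | 2.0 | yes, equal to it |
| Fish oil | either (3) | 3 pills | 3 + 3 = 6 pills | 2.0 | yes, equal to it |

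The supplement with the precaution has the largest proportional rise, and it occurs at the evening intake.

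**With a two-pill limit on the three-pill regimen.**

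- Missed morning: evening intake = 1 scheduled + 1 made up = 2 pills; 1 pill skipped.
- Missed evening: next morning = 2 scheduled + 0 made up = 2 pills; 1 pill skipped.

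**Pills lost.** Taking the six-month stage as 26 weeks, 26 × 7 × 3 = 546 pills. One skipped pill is 1/546 = 0.18%; two are 2/546 = 0.37%.

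**The case against.** The best reply is that nothing here is contradictory. The potassium split is the routine schedule, and the make-up rule is a permissive exception for occasional misses. The ceiling follows closely on the potassium sentence and openly accepts a full daily dose at one time, so it could be a deliberate trade of some tolerability for compliance. Three pills cannot be halved, so an uneven split was unavoidable, and the irritation clause may explain only why the larger part falls in the morning. The ratio of 3.0 also follows from the uneven split alone: after a make-up, every regimen reaches 100% of its daily dose. People with peptic ulcer or other chronic gastrointestinal disease are excluded, side effects are reviewed at each follow-up visit, and the counselor or the guidelines, which are not shown, may already give stricter advice.

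Much of this stands. It is not a strict contradiction, harm is not shown, and the safeguards lower the stakes. But if the clause only explains why the larger part is in the morning, three evening pills reverse exactly that arrangement. Neither the exclusions nor the side-effect review changes what a participant is told to do after a missed dose. Counselors and guidelines could add an exception, but they would be departing from the Protocol's own text, which gives none. Nor does the Protocol say that the trade was intended for potassium.

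**Conclusion.** The concern holds and is minor. As written, the make-up rule permits an evening potassium intake of 60 mmol against a scheduled 20 mmol, which undoes the stated precaution on either reading of its purpose. The morning counterpart, 60 against 40 mmol, matters on one reading only.

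The conclusion rests on the Dosages text and Table 11 alone. How often it would happen, and how much irritation it would cause, cannot be judged from the Protocol. It is confined to make-up days on the potassium regimen. Table 1 estimates 207 participants on active potassium; that is the size of the group, not the number affected. If the unseen participant guidelines already restrict potassium make-ups, the practical risk is smaller, but the Protocol should still be brought into line with them.

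**What to change.** Add one sentence to the Dosages section and to the participant guidelines: *On the three-pill regimen, never take more than two pills at one time; skip any made-up pill beyond that.* Apply it to active and placebo potassium alike. Table 11 gives three pills a day to potassium only, so wording the limit by pill count reaches the right participants, does not separate active from placebo, and leaves the pill coding intact. No intake is added outside the morning and evening schedule, and no intake exceeds the two pills already accepted each morning.

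The cost is one pill (20 mmol) not recovered per single missed dose, 0.18% of the 26-week supply, which works slightly against the compliance aim. One limitation remains: after a missed morning dose the evening intake is two pills, still above the scheduled one. If the aim was to keep the evening intake small, the stricter choice is to allow no potassium make-up at all. That loses two pills (0.37%) per missed morning and one (0.18%) per missed evening. The sponsor should state which aim was meant and choose accordingly.
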